9.5 Primary Outcome Analysis

The primary analysis is the validation of existing CDRs. The Wells DVT score will be computed in all participants with suspected DVT, and both the Wells' PE score and revised Geneva score will be computed in participants with suspected PE. Calibration will be assessed by comparing predicted and observed rates of confirmed VTE (Hosmer-Lemeshow 'goodness-of-fit test'), and discrimination will be assessed using the area under the receiver operating characteristics curve (c-statistic). Further, the proportion of participants with the combination of a non-high clinical probability and negative D-dimer test, and the false-negative rate of this combination (ie the proportion of participants with confirmed recurrent VTE among those with a non-high clinical probability and negative D-dimer) will be estimated along with their 95% confidence intervals.

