15. APPENDICES

Appendix A: Current Clinical Decision Rule for Suspected DVT

Wells Rule for Suspected DVT

[figure not shown]
Clinical characteristics	Points	
Active cancer (patient receiving treatment for cancer within the previous 6 mo or currently receiving palliative treatment)	+ 1	
Paralysis, paresis, or recent plaster immobilization of the lower extremities	+ 1	
Recently bedridden for 3 days or more, or major surgery within the previous 12 wk requiring general or regional anaesthesia	+ 1	
Localized tenderness along the distribution of the deep venous system	+ 1	
Entire leg swollen	+ 1	
Calf swelling at least 3 cm larger than that on the asymptomatic side (measured 10 cm below tibial tuberosity)	+ 1	
Pitting edema confined to the symptomatic leg	+ 1	
Collateral superficial veins (nonvaricose)	+1	
Previously documented deep-vein thrombosis	+1	
Alternative diagnosis at least as likely as deep-vein thrombosis	-2	
Total score	Clinical probability	Prevalence of DVT
< 2 points	DVT unlikely	5.5 % (95%CI: 3.8 to 7.6%)
≥ 2 points	DVT likely	27.9 % (95%CI: 23.9 to 31.8%)

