Appendix B: Current Clinical Decision Rules for Suspected PE

Wells Rule for Suspected PE

Wells score		Revised Geneva score			
Active cancer	+ 1	Age > 65 years	+ 1		
Hemoptysis	+ 1	Active cancer	+ 2		
History of previous DVT or PE	+ 1,5	Hemoptysis	+ 2		
Heart rate > 100 /min	+ 1,5	History of previous DVT or PE	+ 3		
Surgery or bedrest \geq 3 days within 1 month	+ 1,5	Surgery or lower limb fracture within one month	+ 2		
Clinical signs or symptoms of DVT	+ 3	Unilateral edema and pain at palpation	+ 4		
No alternative diagnosis as or more likely than PE	+ 3	Spontaneously reported calf pain	+ 3		
		Heart rate			
		75-94 / min	+ 3		
		\geq 95 / min	+ 5		
Clinical Probability	Total Score	Prevalence of PE	Clinical Probability		
Low	< 2	5.7 (3.7-8.2)	Low	0-3	9.0 (7.6-10.6)
Intermediate	2-6	23.2 (18.3-28.4)	Intermediate	4-10	26.2 (24.4-28.0)
High	> 6	49.3 (42.6-56.0)	High	\geq 11	75.7 (69.0-81.8)
Unlikely	\leq 4	8.4 (6.4-10.6)			
Likely	> 4	34.4 (29.4-39.7)			

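### The primary calibration test leaves its predicted rates, grouping and reference distribution unstated, and the standard Hosmer-Lemeshow reference does not suit rules with two or three published category rates

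*Combined protocol and SAP*

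**What the plan says.** Section 9.5 states: "The primary analysis is the validation of existing CDRs". For DVT, "The Wells DVT score will be computed in all participants with suspected DVT"; for PE, both the Wells PE and revised Geneva scores are calculated. On calibration it says "Calibration will be assessed by comparing predicted and observed rates of confirmed VTE" and names the "Hosmer-Lemeshow 'goodness-of-fit test". It does not say where the predicted rates come from, how participants are grouped, which Wells PE version applies, or what degrees of freedom and significance level are used. The one precision statement in that section, "will be estimated along with their 95% confidence intervals", concerns the combination of non-high probability with a negative D-dimer, not calibration.

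The predicted rates in the documents are one per risk category:

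- Wells DVT (Appendix A), two categories: unlikely "5.5 % (95%CI: 3.8 to 7.6" and likely "27.9 % (95%CI: 23.9 to 31.8" (per cent, with 95% CI).
- Revised Geneva (Appendix B), three categories: 9.0%, 26.2% and 75.7%, the last printed as "75.7 (69.0-81.8".
- Wells PE (Appendix B), both a three-level set (5.7%, 23.2%, 49.3%) and a two-level set (8.4%, 34.4%).

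No predicted rate is given for individual point values.

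**The concern.** The Hosmer-Lemeshow test is normally used to check a logistic model in the data that produced it. Its usual reference, chi-square on g-2 degrees of freedom, allows for that fitting. External validation is different: the published rates are set beforehand and nothing is estimated. An analyst who runs the named test in its standard form meets one of two problems:

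- With the published rates and g-2, there is no P value for a two-category rule, and the test is badly mis-sized for a three-category rule.
- With a model refitted on the risk category, the published predictions are replaced by the study's own, so the existing rule is no longer what is tested.

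The stake is whether the calibration result means what it says. The choice also carries into section 9.5.2, which compares the new rule with the existing ones on the same indices. The new rule will have been fitted in this sample and the existing ones will not, so a single reference cannot suit both.

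**Working it through.** **The plan's own figure.** 100/0.29 = 344.8, rounded up to 345 with suspected DVT; 100/0.25 = 400 with suspected PE; 345 + 400 = 745, as stated in section 9.2. The plan gives no figure for the calibration test, so a 5% level is assumed below.

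**Statistic.** With n_j participants, O_j events and published rate p_j in category j:

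X² = Σ (O_j − n_j p_j)² / [n_j p_j (1 − p_j)].

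If the p_j are fixed and correct, X² is approximately chi-square on g degrees of freedom.

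**Step 1: published rates referred to g-2.**

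- g = 2: 2 − 2 = 0 degrees of freedom, so no P value exists.
- g = 3: the 5% critical value on 1 degree of freedom is 3.84, and P(chi-square on 3 df > 3.84) = 27.9%.
- Simulation with the Appendix B rates as truth, 400 participants, several assumed category mixes and 200,000 studies each: 26.3% to 27.8%.

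**Step 2: published rates referred to g, treated as exact.** The same simulations give 4.9% to 5.2% for three categories and 4.7% to 5.0% for two (345 or 400 participants). The test is then correctly sized.

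**Step 3: published rates referred to g, with their sampling error.** Take SE_j = (upper − lower)/3.92 from the printed intervals. The variance of O_j − n_j p_j then grows by the factor 1 + n_j SE_j² / [p_j (1 − p_j)].

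Example: three-level Wells PE, intermediate category, assumed 64% of 400 = 256 participants. SE = (0.284 − 0.183)/3.92 = 0.0258. Factor = 1 + 256 × 0.0258² / (0.232 × 0.768) ≈ 1.95.

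Simulated false rejection on g degrees of freedom, when the true rates hold and the published rates carry this error:

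| Rule | Assumed shares | Error ignored |
|---|---|---|
| Revised Geneva | 26/64/10% | 7.8% |
| Wells PE, three-level | 26/64/10% | 15.4% |
| Wells DVT | 25/75% | 10.9% |
| Wells PE, two-level | 25/75% | 14.4% |

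Other mixes took three-level Wells PE to about 16%. With n_j² SE_j² added to each denominator, false rejection was 5.1% to 5.6% in every mix tried. All shares are assumptions. The 26% low share is quoted in section 2.2 for the Geneva score in an earlier post-hoc analysis and may not carry over to the revised Geneva.

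**Step 4: refitting on the risk category.**

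- Two categories: two parameters fit two proportions exactly, so X² = 0 whatever the published risks.
- Three categories scored 0, 1, 2: the Geneva logits are −2.31, −1.04 and 1.14, with gaps of 1.28 and 2.17. Doubling every odds adds ln 2 = 0.69 to each logit and leaves the gaps unchanged, so the intercept absorbs the whole shift. In simulation the refitted test rejects in about a third of studies whether the published rates are true or every odds is doubled. It responds to the unequal gaps, not to wrong risks.
- If the fitted straight line is the true model, 1 degree of freedom is correct for the refit (simulated size 4.9%). The refit is a valid test of a different question.

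**The case against.** A reader might infer that the test cannot be applied to these rules. That does not follow: on g degrees of freedom, with published rates treated as exact, it works for two and three categories (step 2).

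A reader might also infer that the plan will falsely reject 28% of the time. The documents do not support that. Section 9.5 gives no degrees of freedom, and the 28% arises only if fixed predictions are paired with a reference meant for fitted ones.

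Nor does the plan say that the primary analysis will refit. Section 9.5 describes validation, and refitting appears separately as secondary recalibration (9.5.1). Because point scores are computed, a refit on points would not be saturated; but the documents give no published rate per point, so that too would not test published risks.

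The consequences are also limited. Calibration is one of three strands in section 9.5, beside the c-statistic and the D-dimer combination. No pass/fail threshold is set, and recalibration is planned for every rule whatever the test shows.

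These objections stand, and they restrict the point to specification and choice of method. They do not remove it: the named test in its standard form is undefined or mis-sized for the only predictions available, and even g degrees of freedom is too liberal when the printed confidence intervals are ignored.

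**Conclusion.** The point holds as a specification gap with a real methodological consequence, and it should be corrected. Depending on a choice the plan leaves open, false rejection of a well-calibrated three-category rule is about 28% (g-2), about 8-15% (g, with sampling error in the published rates ignored) or about 5% (g, with that error included). For two-category rules, g-2 gives no P value at all. A refit on category cannot detect a uniform shift in odds from the published risks.

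The 0 degrees of freedom follows from the group count alone; the 28% also needs the 5% level. The 8-15% further assumes the category shares and takes standard errors from the printed intervals. None of these figures is a prediction of what the sponsor will do.

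**What to change.** In section 9.5:

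1. State that the predicted rates are the Appendix A and B category prevalences, used without refitting, and name the Wells PE version.
2. Make the primary calibration result, for each rule and category, the observed VTE proportion with exact 95% CI beside the published prevalence and its interval, plus the observed/expected ratio. With two or three groups this shows the direction and size of any miscalibration, which a P value does not.
3. If a test is kept, use the Pearson statistic on g degrees of freedom (2 for Wells DVT, 2 or 3 for Wells PE, 3 for revised Geneva), with n_j² SE_j² added to each category's variance, and state the significance level.
4. In section 9.5.2, say which reference applies to the new rule, since it will be fitted in this sample.

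The cost is a few sentences and slightly more analysis work, with no new data or participants. Adding the variance makes the test somewhat less sensitive, as it should be when the published rates are themselves estimates.

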9.6 Secondary Outcome Analysis

9.5.1 Recalibration / minor adjustment to existing rules

Recalibration

For each existing CDR, a multivariate regression analysis including all predictors from the CDR will be conducted. The regression coefficients obtained from this model in our sample will be examined to evaluate whether changes in the points given to each predictor in the rule need to be modified in patients with a suspected recurrent VTE.

Minor adjustments

For each existing CDR, a multivariate regression analysis including all predictors from the CDR will be performed. Candidate predictors will also be included in the analysis, but keeping in the model predictors from the CDR. Should one or two candidate predictors significantly improve risk stratification, a modified score could be proposed for patients with suspected recurrent VTE. Potential improvements in classification will be assessed using the Net Reclassification Improvement and the Integrated Discrimination Improvement indices.

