1.2 Secondary Objectives

- To assess the utility of recalibrating the existing clinical decision rules.
- To derive a new CDR, specific to patients with a suspected recurrent VTE, and to assess whether this CDR would improve risk stratification as compared with existing CDRs.
- To assess the accuracy of D-dimer testing in patients with suspected recurrent VTE both on and off anticoagulation.
- To evaluate the accuracy of current CDRs in patients on anticoagulant therapy at the time of suspected recurrent VTE.

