9.5.2 Derivation of a new CDR

Univariate Analysis

Univariate analysis will be used to assess the association between each variable and VTE recurrence. This process will aid selection of the best variables for the multivariate analysis. The appropriate univariate technique will be chosen according to the type of data.

Multivariate Analysis

Multivariate analysis will derive one model to predict recurrent VTE. Those variables found to be strongly associated with the outcome measure ($P<0.05$), by the univariate analysis and have good inter-observer reliability ($\kappa >0.6$), will be combined using logistic regression. For continuous and ordinal variables various cut-points will be examined to determine the optimal cut-point(s). The derived CDR must be easy to use by clinicians and therefore should contain as few variables as possible. Thus, only the most informative variables will be kept in the final model. Points for the score will be attributed according to regression coefficients. The CDR will be presented in clear narrative form that does not require computation or use of statistical aids. Discrimination and calibration of the new CDR will be estimated and compared to those obtained with existed/modified CDRs using the same indices as described above.

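### The recalibration step re-weights every item and plans no calibration intercept or slope, so the simplest update, which keeps points and classes, is never estimated

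*Combined protocol and SAP*

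**What the plan says.** Section 1.2 sets a secondary objective: "To assess the utility of recalibrating the existing clinical decision rules". Section 9.5.1 gives the method under its Recalibration heading: "For each existing CDR, a multivariate regression analysis including all predictors from the CDR will be conducted". The fitted coefficients are examined to see "whether changes in the points given to each predictor in the rule need to be modified in patients with a suspected recurrent VTE". The Minor adjustments step reuses that regression and extends it: "Candidate predictors will also be included in the analysis, but keeping in the model predictors from the CDR".

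Calibration itself is covered in Section 9.5: "Calibration will be assessed by comparing predicted and observed rates of confirmed VTE", with Hosmer-Lemeshow as the only named summary. The c-statistic covers discrimination. That section promises 95% CIs only for the proportions based on non-high probability with a negative D-dimer. Section 9.5.2 compares the new rule with existing and modified rules "using the same indices as described above".

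No section plans a calibration intercept, a calibration slope, or any model with the existing rule's prediction as a single term. The appendices give points per item and a prevalence per class, but no logistic equation. Appendix B lists both a two-class and a three-class set of prevalences for Wells PE, and Section 9.5 does not say which supplies the predictions.

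**The concern.** A published rule can fit badly here in different ways. Baseline risk may differ, with the rule separating patients as well as before. The rule may be weaker overall. Or particular items may have lost value; Section 2.2 anticipates this for leg symptoms shared with post-thrombotic syndrome. The first two call only for new class rates, and the third bears on the points.

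The plan goes straight from a global test to a refit of every item. Hosmer-Lemeshow gives a p-value and no estimate of shift or weakening. The refit has up to ten free coefficients, no stated criterion, and no original log-odds in the documents to compare with. The least costly update is skipped, so the objective would be answered only for re-weighting.

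A smaller defect is that the refit is to include all items of each rule. Every participant has a prior VTE (Section 4.2), so the prior DVT or PE item in Wells PE and revised Geneva (Appendix B) is constant and its weight cannot be estimated.

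**Working it through.** **Plan's own figures (Section 9.2).** 100/0.29 = 344.8, so 345 DVT; 100/0.25 = 400 PE; total 745. These reproduce.

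**Is the refit too large for the data?** Not by the plan's rule of 5 to 10 events per predictor. With 100 events: Wells DVT 100/10 = 10; Wells PE 100/7 ≈ 14 (100/6 ≈ 17 without the constant item); revised Geneva, counting two heart-rate levels, 100/9 ≈ 11 (100/8 = 12.5).

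**How precise is one item?** SE ≈ 1/√(N·p(1−p)·q(1−q)), with q the item frequency (assumed). For DVT, 345 × 0.29 × 0.71 = 71.0. At q = 0.5 the SE is 1/√(71.0 × 0.25) = 0.24; at q = 0.05 it is 1/√(71.0 × 0.0475) = 0.54.

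**Worked example, Wells DVT.** Class rates are 5.5% and 27.9% (Appendix A). Their logits are −2.844 and −0.949, a gap of 1.894. Assume 70% *likely*: 104 *unlikely* and 241 *likely*. Published rates predict 104 × 0.055 = 5.72 and 241 × 0.279 = 67.24 events.

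Let true rate = expit(a + s·logit(published rate)), with a solved so that 29% are confirmed.

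- Pure shift, s = 1, a = 0.455: rates 8.4% and 37.9%, expected events 8.74 and 91.31.
- Log-odds halved, s = 0.5, a = −0.177: rates 16.8% and 34.3%, expected events 17.49 and 82.56.

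Hosmer-Lemeshow at these counts is Σ(O−E)²/[E(1−rate)], with denominators 5.72 × 0.945 = 5.405 and 67.24 × 0.721 = 48.48.

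- Shift: 3.02²/5.405 + 24.07²/48.48 = 1.7 + 12.0 = 13.6.
- Halved: 11.77²/5.405 + 15.32²/48.48 = 25.6 + 4.8 = 30.5.

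Both exceed 5.99 (2 df), so rejection does not say which occurred.

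For two classes the slope is the observed logit difference divided by 1.894, and its SE is √(Σ[1/events + 1/non-events])/1.894.

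- Shift: √(1/8.74 + 1/95.26 + 1/91.31 + 1/149.69)/1.894 = 0.20, so 1.00 with 95% CI 0.61 to 1.39.
- Halved: √(1/17.49 + 1/86.51 + 1/82.56 + 1/158.44)/1.894 = 0.16, so 0.50 with 95% CI 0.19 to 0.81.

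**Simulation, Wells DVT** (20,000 runs per cell; class mixes assumed; runs without a finite slope counted as not excluding 1):

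| % *likely* | HL rejects: shift | HL rejects: halved | Slope CI excludes 1: shift | Slope CI excludes 1: halved |
|---|---|---|---|---|
| 60 | 99% | 99.9% | 5% | 92% |
| 70 | 90% | 99% | 4% | 85% |
| 80 | 61% | 89% | 3% | 70% |
| 90 | 25% | 57% | 3 to 4% | 46% |

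The intercept CI excludes 0 about equally often in both cases (about 99.5, 93, 71 and 28%). It sizes the shift and does not separate the two cases.

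**PE rules, N = 400, 25% confirmed, assumed mixes.**

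- Wells PE, two-class rates (40 to 80% *likely*): Hosmer-Lemeshow 8 to 84% (shift) against 77 to 99% (halved); slope 3 to 5% against 66 to 95%.
- Wells PE, three-class rates (2 to 26% low, 5 to 30% high): Hosmer-Lemeshow 6 to 59% against 28 to 92%; slope 5% against 31 to 96%. The choice of rate set therefore matters.
- Revised Geneva, same mixes: Hosmer-Lemeshow 6 to 100% against 72 to 100%; slope 4 to 5% against 67 to 100%.

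**What the slope misses.** Weaken only the three Wells DVT items named in Section 2.2 (calf diameter, leg swelling, deep-vein pain). Assumptions: odds ratio 1.5 to 2.5 per point, item frequencies 5 to 60%, class rates from a source population with 16% prevalence and 10% prior DVT, and 55 to 63% *likely*. With the three items halved, the class slope is about 0.90 and its CI excludes 1 in 7 to 12% of runs. With them at zero, it is about 0.76 and 15 to 48%.

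**Constant item.** In both PE rules the prior-VTE item equals 1 for everyone, so it is aliased with the intercept. In Wells DVT the item is "Previously documented deep-vein thrombosis", which varies because a participant may have had only a PE.

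**The case against.** Section 9.5 already compares predicted with observed rates, so a gross departure would be seen. For a two-class rule, intercept and slope are an exact re-expression of the two class rates. This stands: there the gain is an estimate with a CI and a stated reading, not new information.

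The refit meets the plan's own events-per-predictor rule, and it is the only planned analysis that shows unequal weakening of a rule's items. This also stands. A reader might infer that the refit is undersized or should be replaced, and the documents do not support that. Nor is it evidence against the refit that, with all items intact, at least one of ten item CIs would exclude its original value in about 40% of runs: 1 − 0.95¹⁰ = 0.40 is ordinary multiplicity, and the plan proposes no such test.

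A reader might also infer that separating shift from slope decides whether the points must change. It does not. If every coefficient is halved, the ratios between coefficients are unchanged, and so are the relative points. Intercept and slope updates both leave each participant's points and class as they were.

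Finally, Section 9.5.1 states what it will do under the heading, so the label hides nothing about the method. What remains is the missing step.

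**Conclusion.** The point holds and is minor. The plan has no direct estimate of baseline shift or of overall weakening, and the update that keeps points and classes is absent from an objective about recalibration. Where weakening is uniform, the slope separates the two cases where Hosmer-Lemeshow does not. Where only a few items weaken, it has little power, so a slope CI containing 1 must not be read as showing that the items are intact.

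All class mixes, item frequencies and odds ratios are assumed, and halving is illustrative; only the class rates, confirmation rates and group sizes come from the documents. That no intercept or slope is planned, and that the prior-VTE item is constant in the two PE rules, follows from the text without assumptions. The finding touches a secondary objective. It does not affect the sample size, data collection or the estimate of the D-dimer rule-out combination.

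**What to change.** 1. **Section 9.5.** Name the published class rates used as predictions, including which Wells PE set. For each rule report observed/expected by class, the calibration intercept (slope fixed at 1, logit of the published class rate as offset) and the calibration slope on that logit, each with a 95% CI. Note that for two-class rules these re-express the class rates. If Hosmer-Lemeshow is kept, use df equal to the number of occupied classes, because the predictions are external.
2. **Section 9.5.1.** Report the intercept-only update, then intercept plus slope, then the planned item refit as a separate re-weighting step. State that the first two change class rates only; that the slope detects overall weakening and not weakening of a few items; that a slope CI containing 1 does not show intact items; and that only the item refit bears on whether points should change.
3. **Both regressions in 9.5.1.** Omit the prior DVT or PE item for Wells PE and revised Geneva, and state that its effect lies in the intercept. Leave Wells DVT as it is.

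Cost: SAP wording only, with no new data and 745 participants unchanged. There are a few more estimates to report. The Wells DVT slope will be imprecise if few participants are *unlikely*: under a pure shift its median SE is about 0.17 at 60% *likely* and 0.39 at 90%, where about 10% of runs have no event among the *unlikely* and so no finite slope.
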